### 7.3.5 Outcome

The outcome will be the nutritional quality of the products "bought" by the participants. Using a nutrient profiling system, the mean nutritional quality of the food products

purchase will be calculated (see section 8.3.4). Secondary outcomes will be energy and nutritional content in the shopping kart.

[figure not shown]

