- 4) **Virtual Shop.** Participants will be randomly assigned to one of the three conditions of the interventions (no labelling, proposal 1 and proposal 2). Participants assigned to proposals 1 and 2 will receive a brief introduction to the corresponding label before entering the virtual shop. Once in the shop, participants will receive virtual money (equivalent to that reported on their usual spending per week). The virtual shop will emulate a real supermarket with the following sections: 1) milk and dairy, 2) beverages, 3) salty snacks, 4) bakery and cereals, 5) ready to eat meals and 6) checkout. There will be no restrictions on the order of access to the sections or the number of visited sections. Within each section, participants will be presented a variety of real products with a gradient in nutritional quality. The products will display the label corresponding to the intervention condition as well as the nutritional quality of the product. These products will be selected by the INSP research team (from the healthiest to the least healthy). Foods will be presented on shelves (emulating a real supermarket environment) and will have similar costs to real life. The price of the products will be derived from the food data base used in the first phase of the project. Participants will have the possibility to explore the frontal side of each product's package. As in previous stages, the frontal side will have all elements, including other quality labels (for example, nutritional or health claims), except for any other FoPNL system (for example GDA's or the Nutritional Distinctive). Participants will be able to buy as much food as they wish, based on their assigned budget. Once the purchases have been made, participants will proceed to the checkout area to make their payment.
- 5) **Feedback purchase.** Each participant will receive feedback on the nutritional quality of their purchases. Using a nutrient profiling system, the mean nutritional quality of the food products purchase will be calculated (see section 8.3.4). Based on this information, the participant will receive shopping tips for the selection of healthy foods based on the nutritional content reported on the back of the package.

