### 7.3.6 Analysis of the Data

The impact of the two label proposals will be evaluated using a linear regression model, where the outcome will be the mean nutritional quality of the products bought, whereas the independent variable will be the intervention group. The model will be adjusted for the main demographic confounders such as age, sex, civil status, having children and educational attainment and chronic disease. Differences will be considered statistically significant when  $p < 0.05$ . Analysis will be carried out using STATA version 14.0.

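### The primary outcome exists only for randomised people who buy something, and an introduction described only for the label arms comes between allocation and purchase, so the regression is open to arm-specific selection of unknown size and direction

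*Combined protocol and SAP*

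**What the plan says.** The order of events is in 7.3.4.1. Consent, eligibility, and demographic and shopping-habit questions (including usual weekly spend) come first. Randomisation follows, at the start of the fourth component, the Virtual Shop. Then: "Participants assigned to proposals 1 and 2 will receive a brief introduction to the corresponding label before entering the virtual shop". No matching step is described for control.

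Inside the shop, participants move freely: "There will be no restrictions on the order of access to the sections or the number of visited sections". On quantity, "Participants will be able to buy as much food as they wish, based on their assigned budget". No minimum purchase is stated.

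Section 7.3.5 defines the primary outcome: "The outcome will be the nutritional quality of the products" bought. It is computed as a mean: "Using a nutrient profiling system, the mean nutritional quality of the food products" purchased. In the linear regression of 7.3.6, "the outcome will be the mean nutritional quality of the products bought", with arm as the independent variable and adjustment for age, sex, civil status, having children, education and chronic disease.

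Neither section defines an analysis set, a rule for abandoned or empty carts, handling of missing outcomes, or reporting of completion by arm. Section 7.3.7 asks for at least 273 participants per group to detect 0.3 points at a significance level of 0.05 with 80% power. It does not say whether these are people randomised or people analysed. Section 9 discusses low response to online tools only as a threat to sample size and power.

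**The concern.** Randomisation makes the groups comparable as allocated. It does not make the subgroups who stay and buy comparable, if staying depends on what happened after allocation. Here something arm-specific happens between allocation and measurement: the introduction, and then the labels themselves. A person who leaves before paying has no value for the outcome, and a linear regression uses only people who have one. Applied literally, 7.3.5 and 7.3.6 therefore compare purchasers with purchasers.

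If the introduction or the labels change who stays, and those who leave would have shopped differently, part of the estimated label effect reflects who remained and not what the label did to choices. Covariate adjustment removes only the part of this selection that the listed variables explain. Section 2.1 names motivation as a key factor in label use and lists interest in health among the related factors. Neither is among the covariates named in 7.3.6, and both could plausibly affect staying as well as choosing. Section 4 says the evidence could be used by decision makers for labelling policy, so a reader needs to be able to rule out selection as the explanation.

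**Working it through.** **Inputs from the documents (7.3.7).** 273 per group; difference 0.3 points; significance level 0.05; power 80%. Two-sided testing and equal allocation are assumed.

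**Input not in the available text.** The SD. The sample-size figure is not shown, so the SD is back-solved:

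SD = 0.3 × √(273/2) / (1.960 + 0.842) = 1.25.

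Forward check: n = 2 × (1.960 + 0.842)² × 1.25² / 0.3² = 272.5, rounded up to 273. The stated figure is thus consistent with SD 1.25 and no allowance for non-completion. That does not confirm it, because the SD was derived from it; a one-sided 0.05 test, for example, would imply SD 1.41.

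**Bias formula.** Suppose a label arm loses an extra fraction q beyond control, and those people's mean would have been g points below that of the people who stay. The full-arm mean is then the stayers' mean minus q × g, so the stayers overstate their arm by

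bias = q × g.

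If the leavers would have shopped better, g is negative and the bias works against the label.

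**False-positive rate with no true effect.** SE = 1.25 × √(1/273 + 1/[273(1 − q)]). The rate is Φ(bias/SE − 1.96) + Φ(−bias/SE − 1.96). It is the same for either sign of the bias. All q and g below are assumptions.

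| Extra loss q | Gap g (points) | Bias | Share of 0.3 | SE | False-positive rate |
|---|---|---|---|---|---|
| 5 points | 0.5 | 0.025 | 8% | 0.108 | 5.6% |
| 10 points | 0.625 (0.5 SD) | 0.0625 | 21% | 0.110 | 8.8% |
| 10 points | 1.25 (1 SD) | 0.125 | 42% | 0.110 | 20.6% |

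**The other direction.** With a true effect of 0.3 and a bias of −0.125, the expected difference is 0.175. Power is then Φ(0.175/0.110 − 1.96) = about 36%. A useful label could be missed as easily as a useless one could be favoured.

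**How far selection alone could go.** To produce the whole 0.3 points with 10 points of extra loss, the gap would have to be 0.3/0.10 = 3 points, or 3/1.25 = 2.4 SD.

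**Sample size, only if 273 counts people randomised.** With equal loss of 10%, 20% or 30% in every arm, power falls to 76%, 71% or 65%. Keeping 273 with a cart needs 273/(1 − loss) = 304, 342 or 390 randomised per group. A larger sample restores power but does not remove the bias.

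**The case against.** The strongest reply is that this is a gap in specification and not a demonstrated bias. The plan nowhere says it will analyse completers only; that follows from what the model does with a missing outcome. The documents give no completion rate and no information on how leavers would shop. The introduction is called brief, and loss after it may be small and equal across arms. All of this stands, and it limits the claim to a risk. It does not remove the risk, because the only step described between allocation and the shop is specific to the label arms.

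Section 7.3.4.1 also presumes purchases: payment follows shopping, and every participant gets feedback on what was bought. Freedom to skip sections is a navigation rule and does not show that an empty cart can be checked out. The supplier may build the shop to prevent it. That is fair for empty checkouts. Leaving before payment remains possible whatever the checkout rule.

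Three stronger readings are tempting and are not supported:

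- **That the bias favours the labels.** A reader might suppose that people with little interest in nutrition leave once a label is introduced. The opposite is equally compatible with the documents; shoppers already confident about healthy choices might leave.
- **That the task is unpaid and dropout therefore high.** Section 7.1.2.4 describes an incentive for the focus groups. Phase 3 is silent on payment, which does not establish that there is none.
- **That the trial is underpowered.** The wording of 7.3.7 can just as well mean analysable participants, and 7.3.3 and 9 describe recruitment aimed at reaching the required number.

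Imputing missing cart means from baseline data might also look like the natural remedy. It assumes that no selection remains once baseline data are taken into account, and the regression already adjusts for much of those data. If leaving depends on how the person would have shopped, imputation leaves most of the problem in place. For someone who chooses to buy nothing, the mean is undefined and not merely missing, so imputing it changes the question.

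**Conclusion.** The concern holds as a structural weakness. The outcome is defined only for purchasers, allocation precedes an introduction described only for the label arms, and the regression as written keeps only randomised people with a purchase. It is therefore exposed to selection if exits differ by arm. The plan provides no data or analysis by which a reader could judge whether that happened.

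The size and direction are unknown. Under the assumed scenarios the effect runs from negligible (0.025 points, 5.6% false positives) to material (0.125 points, about 21%). The point-scale figures and the first row's rate rest on SD 1.25, which is back-solved and not stated; the rates for gaps set in SD units do not depend on it. The power loss is conditional on 273 meaning people randomised. The structural point depends on none of these figures. The sponsor should act on it because the shop is still to be built and the remedies are cheap at that stage.

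**What to change.** 1. **7.3.4.1, introduction.** Give control a neutral introduction of similar length before the shop. This reduces arm-specific exits but cannot remove them, since the content still differs and labels may prompt exits inside the shop.
2. **7.3.4.1, logging.** Require the shop to record entry, cart contents and checkout for every randomised person.
3. **7.3.6, reporting and sensitivity.** Report by arm the numbers randomised, entering the shop and checking out. Compare completers with non-completers on the data collected before allocation. Add a delta (tipping-point) analysis that shifts the assumed mean of people without an outcome in both directions, and state how large a shift would change the conclusion. Use abandoned-cart contents as a further sensitivity analysis and not as the primary outcome, because a partial basket depends on which sections had been visited. Do not rely on imputation from baseline covariates as the main remedy.
4. **7.3.7.** State that 273 per group means participants with an analysable cart.

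The cost is one neutral screen, a logging requirement in the supplier's specification and a little extra analysis. If item 4 changes the sponsor's reading of 273, somewhat more people must be randomised, in proportion to the non-completion expected.

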### 7.3.6 Analysis of the Data

The impact of the two label proposals will be evaluated using a linear regression model, where the outcome will be the mean nutritional quality of the products bought, whereas the independent variable will be the intervention group. The model will be adjusted for the main demographic confounders such as age, sex, civil status, having children and educational attainment and chronic disease. Differences will be considered statistically significant when  $p < 0.05$ . Analysis will be carried out using STATA version 14.0.

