### **7.3.4 Intervention**

The intervention will consist on an on-line purchase simulation with different labelling systems on food products. Participants will be randomly assigned to one of the three conditions using a randomization program: Control group, (no front-of-pack labeling), Label Proposal 1, and Label Proposal 2. Due to the nature of the intervention there will be no blinding of the intervention.

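### Section 7.3.6 names no variance estimator for the three-arm regression; under a common error variance, pairwise tests depart modestly from 5% if a label changes the spread of the outcome

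*Combined protocol and SAP*

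**What the plan says.** Section 7.3.4 randomises participants to three conditions: "Control group, (no front-of-pack labeling), Label Proposal 1, and Label Proposal 2". Section 7.3.6 sets out the analysis: the effect of the two labels will be "evaluated using a linear regression model", in which "the outcome will be the mean nutritional quality of the products bought, whereas the independent variable will be the intervention group". On covariates it says "The model will be adjusted for the main demographic confounders such as age, sex, civil status, having children and educational attainment and chronic disease". Significance is at p<0.05, in Stata 14.0. The section does not mention robust or arm-specific variances, weighting by the number of products, a check of residual variance, or which arm contrasts will be tested.

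Each outcome value is one mean per participant over a self-chosen set of products. Section 7.3.4.1 says "Participants will be able to buy as much food as they wish, based on their assigned budget", and on the shop's layout "There will be no restrictions on the order of access to the sections or the number of visited sections". The budget equals the participant's own reported weekly spending. It is collected in step 3 of the virtual environment, before assignment in step 4.

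**The concern.** A linear regression with default standard errors estimates one residual variance from all participants. With two equal arms this does no harm to the single comparison, because the pooled variance is the average of the two variances that the comparison needs. With three arms the pooled value also contains the arm outside the comparison. If that arm is more variable than the other two, the standard error is too large; if it is less variable, the standard error is too small. Equal arm sizes do not cure this.

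A label could change the spread in two ways. It could move some shoppers' choices and not others', or it could change how many products are bought within the budget. The trial's hypothesis is that labels alter choices, so equal spread is an assumption, and the plan neither states nor checks it. What is at stake is whether a pairwise test at p<0.05 really has a 5% error rate, and whether the planned 80% power applies to each comparison.

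**Working it through.** **Inputs.** From section 7.3.7: at least 273 per group, a difference of 0.3 points, significance level 0.05, power 80%. Assumed: two-sided testing and 1:1:1 allocation, neither of which is stated. The text gives no SD (Figure 7 was not readable here and may show one), so the SD is also assumed.

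**The plan's own figure.** 273 cannot be reproduced from stated inputs alone. Solving n = 2(1.960 + 0.842)²·SD²/0.3² for n = 273 gives SD² = 273 × 0.09 / (2 × 7.849) = 1.565, so SD = 1.25. Putting 1.25 back in gives n = 273 and power 80.1%. This is the control SD used below.

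**Type I error under a common variance.** For arms i and j with third arm k, all of size n:

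- variance used by the test: (2/n) × (s_i² + s_j² + s_k²)/3
- true variance of the difference: (s_i² + s_j²)/n
- R = used/true = (2/3) × [1 + s_k²/(s_i² + s_j²)]
- true type I error = 2 × [1 − Φ(1.96 × √R)]

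Covariates are left out. Randomisation makes them nearly unrelated to arm, so the SDs can be read as residual SDs.

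**Worked case, SDs 1.25/1.0/1.0 (control/label 1/label 2).** The mean of the three variances is (1.5625 + 1 + 1)/3 = 1.1875.

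- Label against control: true mean variance (1.5625 + 1)/2 = 1.28125; √(1.1875/1.28125) = 0.963; 1.96 × 0.963 = 1.887; error 5.9%.
- Label against label: true mean variance 1; √1.1875 = 1.090; 1.96 × 1.090 = 2.136; error 3.3%.

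**Range of assumed SDs.**

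| SD control / label 1 / label 2 | Control vs label 1 | Control vs label 2 | Label 1 vs label 2 |
|---|---|---|---|
| 1.25 / 1.25 / 1.25 | 5.0% | 5.0% | 5.0% |
| 1.25 / 1.125 / 1.125 | 5.4% | 5.4% | 4.2% |
| 1.25 / 1.375 / 1.375 | 4.7% | 4.7% | 5.7% |
| 1.25 / 1.0 / 1.0 | 5.9% | 5.9% | 3.3% |
| 1.25 / 1.5 / 1.5 | 4.4% | 4.4% | 6.3% |
| 1.25 / 1.25 / 1.0 | 6.6% | 4.2% | 4.2% |
| 1.25 / 1.25 / 1.5 | 3.6% | 5.7% | 5.7% |

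**Upper limit.** R is smallest when s_k = 0, where R = 2/3. Then 1.96 × √(2/3) = 1.600 and the error is 11.0%. No set of SDs exceeds this at equal n.

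**Cart size as the cause.** Assume 10 products per cart in control, half of the outcome variance arising within carts, and both labels reducing carts to 8. The errors are 4.8% (label against control) and 5.4% (label against label). Reducing carts to 5 gives 4.3% and 6.5%. When cart size varied between participants with the same distribution in every arm, the simulated error was 5.0%.

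**Power.** With SDs 1.25/1.25/1.5, control against label 1 has 76.0% power under the common variance and 80.1% with arm-specific variances. The loss comes only from the third arm.

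**Unequal arms.** With 200/310/310 participants and SDs 1.25/1.0/1.0, label against control is at 7.1%.

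**Check of the remedy.** In simulations of 100,000 trials per scenario at 273 per arm, without covariates, arm-specific variances held every pairwise test at 4.8% to 5.1%. HC3 itself was not simulated. In a model with arm terms only, it gives each arm mean the variance s²/(n − 1), which is 273/272 = 1.004 times the arm-specific value, so the result carries over.

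**The case against.** The strongest objection is that nothing in the documents shows unequal spread. They give no SDs by arm and no data on cart size, and they do not say that labels should change either. Every figure above other than the equal-SD row depends on an assumption. This stands, and it is why the point is conditional.

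A reader might infer that the outcome averages over an unlimited number of products and that this alone spoils the tests. The documents do not support that. Section 7.3.4.1 leaves the number and order of sections free, but purchases are capped by a budget reported before assignment, which randomisation balances in expectation. Varying cart size does no harm unless the variance differs between arms. Cart size is also a weak route to large effects: even if all variance arose within carts, taking the SD from 1.25 to 1.0 would need 1.5625 times as many products on the same budget. A change in which products are chosen is the more plausible route.

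A reader might also infer that the plan chose a pooled variance. It did not; section 7.3.6 is silent, and robust standard errors are compatible with its wording. The pooled variance is what follows if the software default is used. Nor does the section list pairwise contrasts. That reading rests on the three-arm design and on section 7.3.7, which sizes the trial for a difference between groups.

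**Conclusion.** The gap is real and minor. Section 7.3.6 leaves the variance estimator open, and the default would make pairwise error rates depend on a third arm whose spread may differ. Under an assumed control SD of 1.25, two-sided tests and equal arms, SD changes of 10% to 20% in one or both label arms move the error to between about 3.3% and 6.6%. The direction depends on the contrast, so this is not a general inflation of false positives. The figures do not support a claim that the planned regression is invalid: the estimated label effects are unaffected, the distortion is bounded at equal n, and it vanishes if the arms have equal spread.

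**What to change.** Add one sentence to section 7.3.6: all arm contrasts from the adjusted linear regression will use heteroscedasticity-robust standard errors (for example Stata regress with vce(hc3)). Name the contrasts in the same place, since the default output shows only comparisons with the reference arm. Reporting the SD of the outcome and the number of products bought by arm would let readers see whether the spread differed.

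The cost is one software option. It needs no extra participants or data, and there is no material loss of power at about 273 per arm. HC3 is one suitable choice; at this sample size another robust or arm-specific estimator would serve equally well.

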#### **7.3.4.1 *Virtual environment for an online shopping simulation***

A supplier will be hired to develop a virtual environment for the on-line shopping simulation. The virtual environment will consist of five components or moments presented

in the following order: 1) Informed Consent, 2) Eligibility, 3) Collection of demographic data and shopping habits), 4) Virtual Store, y 5) Purchase feedback.

- 1) **Informed Consent.** Before data collection, participants will be asked to give their consent to be part of the study through an Informed Consent Letter (See Appendix). Participants will not be able to give their consent until they read all the consent form (scroll all the way down).
- 2) **Eligibility.** Participants will be asked to confirm they meet the established eligibility criteria. (See section 8.3.2)
- 3) **Demographic data collection. The same** initial questionnaire used in Phase 1 will be used to collect general demographic information (age, sex, information contact), consumption and purchase habits, as well as a series of questions to determine the individual socioeconomic level (Appendix 1). Additionally, information on habitual expenses per week at the supermarket will be requested.

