### 7.3.7 Sample size

Based on previous experiences [46], and considering a significance level of 0.05 and a statistical power of 80%, at least 273 participants per intervention group will be required to detect a difference of 0.3 points in the mean nutritional quality between intervention groups (Figure 7).

**Figura 7.** Tamaño de muestra necesario para detectar una diferencia mínima en nutricional.

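### Free improvement: the Phase 3 primary regression could use a closed covariate list that adds the shopping habits, socioeconomic level and weekly spending reported before randomisation

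*Combined protocol and SAP*

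**What the plan says.** Section 7.3.6 specifies a linear regression in which "the outcome will be the mean nutritional quality of the products bought, whereas the independent variable will be the intervention group". On covariates it says: "The model will be adjusted for the main demographic confounders such as age, sex, civil status, having children and educational attainment and chronic disease". It names nothing else and does not state how the covariates are coded.

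Section 7.3.4.1 describes what participants report on the website. The components come "in the following order: 1) Informed Consent, 2) Eligibility, 3) Collection of demographic data and shopping habits), 4) Virtual Store". Component 3 reuses the initial Phase 1 questionnaire, which covers age and sex, then "consumption and purchase habits, as well as a series of questions to determine the individual socioeconomic level (Appendix 1"). It also adds a spending question: "Additionally, information on habitual expenses per week at the supermarket will be requested". Assignment is described under component 4: "Participants will be randomly assigned to one of the three conditions of the interventions (no labelling, proposal 1 and proposal 2"). In the shop, "participants will receive virtual money (equivalent to that reported on their usual spending per week").

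Section 7.3.7 gives the size of the trial: "at least 273 participants per intervention group will be required to detect a difference of 0.3 points", at a significance level of 0.05 and 80% power.

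**The concern.** In a randomised comparison, baseline covariates are there to explain outcome variance. Random assignment already deals with confounding. Choosing covariates as confounders leads naturally to a demographic list and passes over variables that may say more about what a person puts in a cart. Here those variables are reported before assignment, so adjusting for them cannot bias the comparison. Weekly spending has a direct link to the task, because it fixes the budget within which the cart is filled.

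Precision is at stake. Outcome variance that these answers could explain stays in the error term of both label-versus-control contrasts. Section 9 itself warns that a low online response could limit sample size and power, so precision that needs no extra recruitment is worth having. The open list has a second cost: the final covariate set could be chosen after the outcome data have been seen.

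**Working it through.** **Timing.** In section 7.3.4.1 the habit, socioeconomic and spending questions sit in component 3 and assignment sits in component 4. All three are therefore pre-randomisation variables.

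**Inputs.** Section 7.3.7 gives n = 273 per arm, a difference of 0.3 points, alpha 0.05 and power 80%. Three assumptions are mine: a two-sided test (sidedness is not stated), equal allocation (the same minimum applies to each arm), and R², the further share of outcome variance that the unnamed variables explain beyond the named covariates.

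**Recovering the plan's figure.** The text gives no SD and the sample size figure is not shown, so the SD is solved backwards:

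SD = 0.3 / [(1.960 + 0.842) × √(2/273)] = 1.251, or about 1.25.

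Putting SD 1.25 back into the usual two-mean formula returns 273 per arm. This shows what the statement implies. It is not an independent confirmation. The standard error of a pairwise contrast is 1.25 × √(2/273) = 0.107.

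**Effect of further adjustment.** Residual SD = 1.25 × √(1 − R²). Power = Φ(0.3 / [0.107 × √(1 − R²)] − 1.960). The number per arm that would give the same precision without the extra covariates is 273 / (1 − R²).

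| Assumed further R² | SE | Reduction in SE | Power at 0.3 points | Equivalent n per arm |
|---|---|---|---|---|
| 0 | 0.107 | none | 80.1% | 273 |
| 0.02 | 0.106 | 1.0% | 80.9% | 279 |
| 0.05 | 0.104 | 2.5% | 82.0% | 287 |
| 0.10 | 0.101 | 5.1% | 84.0% | 303 |
| 0.20 | 0.096 | 10.6% | 88.0% | 341 |

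The SD cancels from the power column: 0.3/SE is fixed at 1.960 + 0.842 by the plan's own 80%, so power depends only on alpha, that 80% and R².

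**Cost of adjustment.** The trial has 3 × 273 = 819 participants at the stated minimum. A covariate term that predicts nothing inflates the variance of a contrast by roughly 1/819 = 0.12%. Five such terms would cost about 0.6% of variance, against a 2% cut in variance if R² were only 0.02.

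**The case against.** The strongest reply is that the gain is unproven. The documents give no R² and no data linking habits, socioeconomic level or spending to the nutritional quality of purchases. At R² = 0.02 power moves by less than one percentage point, and near zero there is no gain. This stands.

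A reader might infer from 7.3.6 that the model is limited to demographic variables and shuts the others out. The text does not support that. The list is introduced as a set of examples, and chronic disease is not a demographic variable. What can be said is that the habit, socioeconomic and spending variables are not named and that the set is not closed.

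A reader might also treat reported habits as close to a baseline value of the outcome. That cannot be shown either. Section 7.1.2.1 describes the questionnaire as a tool for exploring eligibility, and the related focus-group criterion is how often categories are bought and consumed. The outcome is the mean profile score of the products chosen. Appendix 1 is not shown, so whether any item captures the quality of usual purchases is unknown. The food categories in section 7.1.1.2 also do not match the shop sections exactly, so frequencies for precisely those sections should not be presumed available.

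Socioeconomic level is partly represented already: education is named in 7.3.6, and schooling of the household's main contributor is one of the eight items of the index in 7.1.2.1. The overlap is partial and does not reach habits or spending. The remark in section 9 that results do not differ by socioeconomic level concerns understanding and acceptability of labels, not what people buy.

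Finally, the documents do not say whether the planning SD is raw or already adjusted. The 80% starting point is therefore the plan's nominal figure, not the known power of the model as written. None of these points shows harm from the change.

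**Conclusion.** This is a free improvement, not an error. Variables plausibly related to the outcome are reported before randomisation and are not named in the primary model. Adjusting for them cannot bias the contrasts and may sharpen them.

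Under the assumptions of a two-sided 0.05 test, equal arms of 273 and nominal 80% power, the gain at 0.3 points runs from nothing at a further R² of 0 to about 8 percentage points of power at 0.20. Those R² values are assumed, and the true gain may be negligible.

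A reader might conclude that the trial as planned is biased, underpowered or certain to lose precision. The documents do not support any of these. Randomisation protects the comparison with or without the extra covariates, the stated 273 per arm does not depend on them, and no figure in the plan shows how much variance they would explain.

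**What to change.** In 7.3.6, replace the open list with a closed list of pre-randomisation covariates, described as prognostic and not as confounders, and state the coding of each. Add to the variables already named:

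- the purchase and consumption habit items, as actually asked in Appendix 1;
- socioeconomic level;
- usual weekly supermarket spending.

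Fix the list before outcome data are opened, and report the unadjusted contrast beside the adjusted one. If any of the three is left out on purpose, say why.

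While making the edit, check that each named covariate is collected in Phase 3. The description in 7.3.4.1 does not list civil status, having children or chronic disease. These appear in the separate questionnaire of 7.1.2.3.2. Appendix 1 may settle this, so it is a matter to reconcile.

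The change is a sentence or two of text. It needs no new participants and no data beyond what component 3 already plans to collect, and it uses a few degrees of freedom out of about 819.
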